11.0 Safety Analysis

11.1 General Considerations

Safety data will be summarized using the safety population. Data will be summarized for the overall population across genotype and across treatment arm.

11.2 Analysis of Adverse Events

Adverse events (AEs) will be coded using the Medical Dictionary for Regulatory Activities (MedDRA). The actual version of the MedDRA coding dictionary will be noted in the clinical study report.

11.2.1 Treatment-Emergent Adverse Events

Treatment-emergent AEs are defined as any AE with an onset date that is after the first dose of study drug and no more than 30 days after the last dose of study drug. Events where the onset date is the same as the study drug start date are assumed to be treatment-emergent. If an incomplete onset date was collected for an AE, the event will be assumed to be treatment-emergent, unless there is other evidence that confirms that the event was not treatment-emergent (e.g., the event end date was prior to the study drug start date).

11.2.2 Tabulations of Treatment-Emergent Adverse Events

For all the summaries in this section, the number and percentage of subjects with treatment-emergent AEs will be tabulated.

Adverse Event Overview

An overview of AEs will be presented that consists of the number and percentage of subjects experiencing at least one event for each of the following treatment-emergent AE categories:

- Any treatment-emergent AE;
- Treatment-emergent AEs with a "reasonable possibility" of being related to DAAs (GLE/PIB);
- Treatment-emergent AEs of Grade 3 or higher;
- Serious treatment-emergent AEs;
- Serious treatment-emergent AEs with a "reasonable possibility" of being related to DAAs (GLE/PIB);
- Treatment-emergent AEs leading to discontinuation of study drug;
- DAA-related treatment-emergent AEs leading to discontinuation of study drug;
- Treatment-emergent AEs of Grade 3 or higher with a "reasonable possibility" of being related to DAAs (GLE/PIB);
- Serious treatment-emergent AEs leading to discontinuation of study drug;

- Treatment-emergent AEs leading to interruption of study drug;
- Treatment-emergent AEs leading to death;
- Deaths.

Adverse Events by System Organ Class and Preferred Term

The number and percentage of subjects with treatment-emergent AEs will also be tabulated by primary MedDRA System Organ Class (SOC) and preferred term (PT) for the summaries listed below. The SOC's will be presented in alphabetical order, and the PTs will be presented in alphabetical order within each SOC.

- Treatment-emergent AEs;
- Serious treatment-emergent AEs;
- Serious treatment-emergent AEs with a "reasonable possibility" of being related to DAAs (GLE/PIB);
- Treatment-emergent AEs leading to discontinuation of study drug;
- DAA-related treatment-emergent AEs leading to discontinuation of study drug;
- Treatment-emergent AEs leading to death.

Subjects reporting more than one AE for a given PT will be counted only once for that term (most severe/highest grade incident for the severity tables and most related incident for the relationship tables). Subjects reporting more than one AE within an SOC will be counted only once for that SOC. Subjects reporting more than one AE will be counted only once in the overall total.

If a subject has an AE with unknown relationship, then the subject will be counted in the relationship category of "unknown," even if the subject has another occurrence of the same event with a relationship present. The only exception is if the subject has another occurrence of the same AE with a relationship assessment of "reasonable possibility." In this case, the subject will be counted under the "reasonable possibility" category.

A listing of treatment-emergent AEs grouped by SOC and PT with subject numbers will be created for each treatment arm.

Adverse Events by Preferred Term

The following summaries of treatment-emergent AEs tabulated according to PT and sorted by the overall frequency across the two treatment arms will be generated:

- Treatment-emergent AEs;
- Treatment-emergent AEs with a "reasonable possibility" of being related to DAAs (GLE/PIB);
- Treatment-emergent AEs of Grade 3 or higher;
- Treatment-emergent AEs of Grade 3 or higher with a "reasonable possibility" of being related to DAAs (GLE/PIB).

Subjects reporting more than one AE for a given PT will be counted only once for that term (most severe/highest grade incident for the severity tables and most related incident for the relationship tables). Subjects reporting more than one AE will be counted only once in the overall total.

Adverse Events by Maximum Severity Grade Level

Treatment-emergent AEs and DAA-related treatment emergent AEs will be summarized by maximum severity grade level of each PT tabulated by SOC. Each AE will be assigned a grade level (Grade 1, 2, 3, 4, or 5) by the investigator. If a subject has an AE with unknown severity, then the subject will be counted in the severity grade level category of "unknown," even if the subject has another occurrence of the same event with a severity present. The only exception is if the subject has another occurrence of the same AE with the highest grade level (Grade 5). In this case, the subject will be counted under the "Grade 5" category.

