6.1.3 Relationship to Study Drug

The investigator will use the following definitions to assess the relationship of the adverse event to the use of study drug:

Reasonable Possibility	An adverse event where there is evidence to suggest a causal relationship between the study drug and the adverse event.
No Reasonable Possibility	An adverse event where there is no evidence to suggest a causal relationship between the study drug and the adverse event.

For causality assessments, events assessed as having a reasonable possibility of being related to the study drug will be considered "associated." Events assessed as having no reasonable possibility of being related to study drug will be considered "not associated." In addition, when the investigator has not reported a causality or deemed it not assessable, AbbVie will consider the event associated.

[figure not shown]
If an investigator's opinion of no reasonable possibility of being related to study drug is given, an "Other" cause of event must be provided by the investigator for the serious adverse event.

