8.1.5.1 Adverse Events

Adverse events will be coded using the Medical Dictionary for Regulatory Activities (MedDRA). The number and percentage of subjects with treatment-emergent adverse events (i.e., any event that begins or worsens in severity after initiation of study drug through 30 days post-study drug dosing) will be tabulated by primary MedDRA System Organ Class (SOC) and preferred term. The tabulation of the number of subjects with treatment-emergent adverse events by severity grade (Grades 1 – 5) and relationship to each study drug will also be provided. Subjects reporting more than one adverse event for a given MedDRA preferred term will be counted only once for that term using the most severe grade for the severity grade table and the most related for the relationship to study drug tables. Subjects reporting more than one type of event within a SOC will be counted only once for that SOC.

Additional analyses will be described in the statistical analysis plan.

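### SAP 11.2.2 tabulates missing causality as unknown and lets an ungraded occurrence displace a known grade, departing from the protocol without declaring it

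*SAP*

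**What the plan says.** SAP 11.2.2 describes how a subject with several occurrences of one preferred term is counted. Its general rule takes the "most severe/highest grade incident for the severity tables and most related incident for the relationship tables". That matches Protocol 8.1.5.1, under which a subject is "counted only once for that term using the most severe grade for the severity grade table and the most related" for the relationship tables.

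Two further rules in SAP 11.2.2 deal with missing information:

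- **Relationship.** "If a subject has an AE with unknown relationship, then the subject will be counted in the relationship category of" unknown, whether or not another occurrence of that event was assessed. Only a reasonable-possibility rating on another occurrence overrides this. The related-event lines and tables are defined by the reasonable-possibility rating, or are labelled DAA-related.
- **Severity**, in the part on maximum grade. An ungraded occurrence puts the subject in the unknown category although another occurrence has a grade. The one way out is given as "The only exception is if the subject has another occurrence of the same AE with the highest grade level (Grade 5".

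Protocol 6.1.3 treats missing causality differently: "when the investigator has not reported a causality or deemed it not assessable, AbbVie will consider the event associated". The same section equates associated with the reasonable-possibility rating. SAP 12.1 lists 11 changes from the protocol; neither rule is among them.

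**The concern.** Safety is part of the primary objective (Protocol 4.1, SAP 4.1), and these tables are its main evidence.

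The causality rule matters more. The protocol gives an event with no causality a definite status: related. The SAP gives it a separate category and then builds every related-event count from the reasonable-possibility category alone. An event that the protocol counts as related would be absent from those counts.

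The severity rule is narrower. A table meant to show each subject's worst grade for a term can show unknown for someone with a documented Grade 3 or 4 event. A reader comparing it with the Grade 3 or higher tables would find numbers that do not agree, with no explanation in the plan.

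**Working it through.** The plan gives no figure on this point, so the check is to apply each document's rule to every combination of known and missing information for one subject and one preferred term.

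**Relationship** (SAP 11.2.2 against Protocol 6.1.3 combined with the most-related rule in Protocol 8.1.5.1)

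| Occurrences of the term | SAP | Protocol |
|---|---|---|
| Missing only | Unknown | Related |
| Missing + no reasonable possibility | Unknown | Related |
| Missing + reasonable possibility | Related | Related |
| No reasonable possibility only | Not related | Not related |

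The documents differ in the first two rows. In both, the subject is outside the SAP's related count and inside the protocol's. The outputs exposed are the related, related serious and related Grade 3 or higher lines of the overview and the corresponding tables by term, and, if DAA-related means reasonable possibility, the DAA-related discontinuation and maximum-grade tables. In an overview line the subject is lost only if no other event puts them there.

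**Severity** (one ungraded occurrence plus one graded occurrence)

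| Known grade | SAP maximum-grade table | Highest known grade |
|---|---|---|
| 1 | Unknown | 1 |
| 2 | Unknown | 2 |
| 3 | Unknown | 3 |
| 4 | Unknown | 4 |
| 5 | 5 | 5 |

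Four of the five known grades are replaced. The rule stands only in the maximum-grade part of SAP 11.2.2. The overview counts a subject with at least one event of Grade 3 or higher, and the Grade 3 or higher table by preferred term follows the general highest-grade rule. On a plain reading both keep the known Grade 3 or 4 event, so the tables can disagree.

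**Size.** SAP 5.1.3 and 11.1 tabulate safety for both arms combined, and SAP 4.2 plans about 80 subjects. One reclassified subject moves a percentage by 1/80 = 1.25 points. At the minimum enrolment by genotype, 15 + 30 = 45, it would be 1/45 = 2.2 points. The number affected is not given. As an assumed range at 80 subjects, 0 to 3 affected subjects move a line by 0 to 3/80 = 3.75 points.

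**The case against.** **The severity rule has a logic.** If one occurrence is Grade 3 and another is ungraded, the true maximum is not known; only a Grade 5 settles it, which explains the single exception. Protocol 8.1.5.1 does not say what to do with a missing grade, and the SAP's stated role is to elaborate the protocol's methods. This stands in part: the rule is at odds with the most-severe-grade principle, but it does not break an explicit protocol rule on missing grades. It still discards information, since the known grade is a lower limit for the maximum.

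**The causality rule may never bite.** Protocol 6.1.3 concerns assessment, and Protocol 8.1.5.1 does not repeat it for tabulation. If the sponsor assigns associated before the tables are run, the unknown category is empty and nothing is lost. That is possible, but the SAP states no such step, and a rule for an unknown category suggests that none is planned.

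**The trigger should be rare.** Protocol 6.1 and 6.1.2 require severity and relationship for every adverse event, Protocol 10.2 has the eCRFs reviewed for completeness, and SAP 4.4 has data cleaned before lock. The severity problem also needs two occurrences of one term in one subject. This stands, although Protocol 6.1.1.1 makes repeat entries foreseeable by asking that a worsening be reported as a new event.

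**Stronger readings that the documents do not support.** A reader might infer that severe events vanish from the safety report. They do not: the Grade 3 or higher tables keep them, and the subject remains visible as unknown in the maximum-grade table. A reader might infer that both rules always favour the drug. Displacing a Grade 1 or 2 event lowers no severe count, and the relationship rule never loses a known related occurrence. A reader might also work out the effect within the roughly 16 cirrhotic subjects, but SAP 12.1 (item 2) confines the safety analyses to the overall population; by arm, SAP 11.2.2 plans only a listing of adverse events.

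**Conclusion.** The point holds, mainly on causality. Followed as written, the SAP leaves out of its related-event counts events that Protocol 6.1.3 treats as related, and it does not declare the departure. This assumes that the sponsor's associated status is not written into the data before tabulation; neither document says that it is.

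The severity half is a smaller, presentational fault confined to the maximum-grade tables: they depart from the highest-grade principle in Protocol 8.1.5.1 and in the SAP itself, and can fail to reconcile with the Grade 3 or higher tables.

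The likely effect is small and may be nil, since it depends on how often grade or causality is missing. The reason to act is that the rules conflict on paper and are cheap to align. Elsewhere the SAP already resolves missing adverse event data cautiously: under SAP 11.2.1 an event with an incomplete onset date is assumed treatment-emergent unless other evidence shows that it was not.

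**What to change.** Change two sentences in SAP 11.2.2:

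1. **Causality.** Count an event whose causality is missing or not assessable as a reasonable possibility in the overview and in every related-event table, as Protocol 6.1.3 implies, with a footnote giving the number so assigned.
2. **Severity.** In the maximum-grade tables, classify each subject by the highest known grade for the term. Use unknown only when no occurrence of that term has a grade, and footnote subjects who also have an ungraded occurrence, so that the uncertainty about the true maximum stays visible.

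If the sponsor prefers to keep either rule, list it in SAP 12.1 with a reason. If associated status is already assigned before tabulation, one sentence saying so would settle the causality half.

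The cost is the two sentences and a small programming change. The downside is that related-event counts may be slightly higher.

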11.2.3 Adverse Events of Special Interest

Adverse events of special interest include the following:

- Hepatic decompensation/hepatic failure events, identified using the AbbVie Product MedDRA Query (PMQ) for Hepatic Decompensation and Hepatic Failure;
- Hepatocellular carcinoma events, identified using the PTs of hepatocellular carcinoma, hepatic neoplasm, hepatic cancer, hepatic cancer metastatic, and hepatic cancer recurrent.

For the hepatic decompensation/ hepatic failure AE of special interest, the number and percentage of subjects experiencing at least one treatment-emergent AE in the search will be presented by SOC and PT and across all SOCs/PTs. In addition, a by-subject listing of treatment-emergent AEs meeting the search criterion will be provided.

For the hepatocellular carcinoma AE of special interest, a by-subject listing of all post-baseline (i.e., including both treatment-emergent and non-treatment emergent) AEs meeting the search criterion will be provided.

11.2.4 Listing of Adverse Events

The following listings of AEs will be prepared:

- All serious AEs (from the time the subject signed the study-specific informed consent through the end of the study),
- Treatment-emergent serious AEs,
- Treatment-emergent AEs leading to discontinuation of study drug,
- Treatment-emergent AEs leading to study drug interruption.
- AEs (treatment-emergent or all, as applicable) in each of the AEs of special interest categories.

11.3 Analysis of Laboratory Data

Data collected from the central and local laboratories, including additional laboratory testing due to a serious AE, will be used in all analyses.

11.3.1 Variables and Criteria Defining Abnormality

Hematology variables to be summarized include: hematocrit, hemoglobin, red blood cell (RBC) count, white blood cell (WBC) count, neutrophils, bands, lymphocytes, monocytes, basophils, eosinophils, platelet count, reticulocyte count, prothrombin time (PT), international normalized ratio (INR), and activated partial thromboplastin time (aPTT).

Chemistry variables to be summarized include: blood urea nitrogen (BUN), creatinine, total bilirubin, direct and indirect bilirubin, alanine aminotransferase (ALT), aspartate aminotransferase (AST), alkaline phosphatase, sodium, potassium, calcium, inorganic phosphorus, cholesterol, total protein, glucose, triglycerides, albumin, chloride, bicarbonate, magnesium, total insulin, gamma-glutamyl transferase (GGT), creatinine clearance (calculated using Cockcroft-Gault formula), and eGFR (calculated using MDRD equation).

Urinalysis variables to be summarized include: specific gravity and pH.

The definitions of toxicity grades for laboratory parameters are presented in [Table 9](#).

Table 9. Definitions of Toxicity Grades 1, 2, 3, and 4 for Laboratory Values

Test	Grade 1	Grade 2	Grade 3	Grade 4
ALT	> ULN – 3 × ULN	> 3 – 5 × ULN	> 5 – 20 × ULN	> 20 × ULN
AST	> ULN – 3 × ULN	> 3 – 5 × ULN	> 5 – 20 × ULN	> 20 × ULN
Alkaline Phosphatase	> ULN – 2.5 × ULN	> 2.5 – 5 × ULN	> 5 – 20 × ULN	> 20 × ULN
GGT	> ULN – 2.5 × ULN	> 2.5 – 5 × ULN	> 5 – 20 × ULN	> 20 × ULN
Total Bilirubin	> ULN – 1.5 × ULN	> 1.5 – 3 × ULN	> 3 – 10 × ULN	> 10 × ULN
Hemoglobin	< LLN – 100 g/L	< 100 – 80 g/L	< 80 g/L	--
White blood cells	< LLN – 3.0 × 10 ⁹ /L	< 3.0 – 2.0 × 10 ⁹ /L	< 2.0 – 1.0 × 10 ⁹ /L	< 1.0 × 10 ⁹ /L
Absolute Neutrophil Count	< LLN – 1.5 × 10 ⁹ /L	< 1.5 – 1.0 × 10 ⁹ /L	< 1.0 – 0.5 × 10 ⁹ /L	< 0.5 × 10 ⁹ /L
Platelet count	< LLN – 75.0 × 10 ⁹ /L	< 75.0 – 50.0 × 10 ⁹ /L	< 50.0 – 25.0 × 10 ⁹ /L	< 25.0 × 10 ⁹ /L
INR	> 1 – 1.5 × ULN	> 1.5 – 2.5 × ULN	> 2.5 × ULN	--
Glucose (increased)	> ULN – 8.9 mmol/L	> 8.9 – 13.9 mmol/L	> 13.9 – 27.8 mmol/L	> 27.8 mmol/L
Glucose (decreased)	< LLN – 3.0 mmol/L	< 3.0 – 2.2 mmol/L	< 2.2 – 1.7 mmol/L	< 1.7 mmol/L
Creatinine	> ULN – 1.5 × ULN	> 1.5 – 3 × ULN	> 3 – 6 × ULN	> 6 × ULN
Creatinine clearance	< LLN – 60 mL/min	< 60 – 30 mL/min	< 30 – 15 mL/min	< 15 mL/min
Cholesterol	> ULN – 7.75 mmol/L	> 7.75 – 10.34 mmol/L	> 10.34 – 12.92 mmol/L	> 12.92 mmol/L
Albumin	< LLN – 30 g/L	< 30 – 20 g/L	< 20 g/L	--

11.3.2 Statistical Methods

The baseline value for clinical laboratory tests will be the last non-missing measurement on or before the day of the first dose of study drug. Values on Day 1 must also be before the time of first dose if time is available. The same baseline value will be used for changes to Treatment Period visits and changes to Post-Treatment Period visits.

Visit Values

For each laboratory parameter listed in Section 11.3.1, values at each visit (baseline and post-baseline, including applicable post-treatment visits) will be summarized with the

sample size, mean, standard deviation, minimum, median, and maximum. Figures presenting mean values over time will be produced.

Change from Baseline

For each laboratory parameter listed in Section 11.3.1, changes from baseline to each post-baseline visit, including applicable post-treatment visits, will be summarized with the sample size, baseline mean; visit mean; and change from baseline mean, standard deviation, minimum, median, and maximum.

Shift Tables

Individual changes in the laboratory parameters listed in Section 11.3.1 will be tabulated using shift tables. Laboratory data values will be categorized as low, normal, or high based on normal ranges of the laboratory used for each sample. Shift tables from baseline to minimum value and maximum value during the Treatment Period will be created. For each parameter, the shift tables will cross tabulate the frequency of subjects with baseline values below/within the normal range to maximum above the normal range and with baseline values within/above the normal range to minimum below the normal range.

Maximum Toxicity Grade

The laboratory parameters listed in Table 9 will be assigned a toxicity grade of 1, 2, 3, or 4. The number and percentage of subjects with a maximum toxicity grade of 1, 2, 3 or 4 during the Treatment Period will be tabulated. To be counted, the post-baseline value must have a toxicity grade that is more extreme than the toxicity grade corresponding to the baseline value. For each laboratory parameter in Table 9, the summary will also include the number and percentage of subjects with a maximum of at least Grade 3. A listing of all relevant laboratory parameters will be provided for each subject who had an increase to Grade 2 or higher for any laboratory variable in Table 9.

Assessment of Hepatic Laboratory Values

The number and percentage of subjects with laboratory values meeting the following criteria during treatment will be summarized:

- Post-nadir (preceding value is lower than the subsequent value) ALT $> 5 \times \text{ULN}$ (regardless of grade change);
- Total bilirubin $\geq 2 \times \text{ULN}$ and $>$ baseline (i.e., a post-baseline value must be more extreme than the baseline value to be considered);
- Post-nadir ALT $> 3 \times \text{ULN}$ and total bilirubin $> 2 \times \text{ULN}$;
- Post-nadir ALT $> 3 \times \text{ULN}$ and total bilirubin $\leq 2 \times \text{ULN}$.

Four listings (one for each bullet above) of all hepatic laboratory values including ALT, AST, total, indirect and direct bilirubin, ratio of direct to total bilirubin, and alkaline phosphatase values will be provided for each subject who met the criterion defined above.

Hepatic Laboratory Abnormalities of Interest

Among the events assessed under "Assessment of Hepatic Laboratory Values," the following criteria are of interest:

- Confirmed post-nadir ALT $> 5 \times \text{ULN}$;
- Post-nadir ALT $> 3 \times \text{ULN}$ and a concurrent total bilirubin $> 2 \times \text{ULN}$ with a direct/total bilirubin ratio > 0.4 .

To support the assessment of hepatic laboratory abnormalities of interest, the following potential events will be summarized:

- Confirmed post-nadir ALT $> 5 \times \text{ULN}$;
- Post-nadir ALT $> 3 \times \text{ULN}$ and total bilirubin $> 2 \times \text{ULN}$ and direct/total bilirubin ratio > 0.4 .

Two listings (one for each bullet) of all hepatic laboratory values including ALT, AST, total, indirect and direct bilirubin, ratio of direct to total bilirubin, and alkaline phosphatase values will be provided for each subject who met the criterion defined above.

For the **assessments of hepatic laboratory values** and **hepatic laboratory abnormalities of potential interest**, the maximum ratio relative to the ULN will be used to determine if subjects meet any of the criteria listed above. The ALT and total bilirubin values do not need to be concurrent in order to meet the defined criteria in statistical summaries. For ALT, the post-baseline value must represent an increase from the first nadir (including baseline) to be counted. First nadir is defined as the last value prior to the first increase. For total bilirubin, a subject will be counted if the post-baseline laboratory value meets the above criteria regardless of the baseline laboratory value (i.e., the post-baseline laboratory value does not need to be worse than the baseline laboratory value), except where noted above. A confirmed post-nadir increase in ALT is defined as two consecutive values of $ALT > 5 \times ULN$ after nadir, either both during treatment or at the final treatment measurement and the next consecutive post-treatment measurement. A single post-nadir ALT value of greater than $5 \times ULN$ followed by lost to follow-up (no additional ALT values) also will be considered (i.e., will not require confirmation). The ratio of direct to total bilirubin will be calculated using the same date/time sample corresponding to the total bilirubin elevation.

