8.1.5.2 Clinical Laboratory Data

Clinical laboratory tests will be summarized at each visit. The baseline value will be the last non-missing measurement prior to the initial dose of study drug. Mean changes from baseline to each post-baseline visit, including Final Treatment Visit, will be summarized descriptively. Changes from baseline to post-baseline in the CTCAE grading of laboratory values will also be summarized.

Laboratory data values will be categorized as low, normal, or high based on reference ranges of the laboratory used in this study. The number and percentage of subjects who experience post-baseline shifts during treatment in clinical laboratory values from low/normal to high and high/normal to low based on the normal range will be summarized.

In addition, the number and percentage of subjects with post-baseline values meeting pre-specified criteria for Potentially Clinically Significant laboratory values or toxicity grades during treatment will be summarized.

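### The shift tables pick each subject's on-treatment minimum or maximum before allowing for differing laboratory ranges, so a borderline out-of-range value can be missed when central and local results are mixed

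*SAP*

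**What the plan says.** SAP 11.3 sets the data source for all laboratory summaries: "Data collected from the central and local laboratories, including additional laboratory testing due to a serious AE, will be used in all analyses".

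Under Shift Tables, SAP 11.3.2 gives the classification rule: "Laboratory data values will be categorized as low, normal, or high based on normal ranges of the laboratory used for each sample". The next sentence gives the values to be tabulated: "Shift tables from baseline to minimum value and maximum value during the Treatment Period will be created". The counting rule refers to those extremes. On the high side it runs from "baseline values below/within the normal range to maximum above the normal range", and on the low side from "baseline values within/above the normal range to minimum below the normal range". The tables cover every parameter listed in SAP 11.3.1.

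Three other places bear on the point:

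- For the hepatic criteria, SAP 11.3.2 says that "the maximum ratio relative to the ULN will be used to determine if subjects meet any of the criteria listed above". That scales each value to its range before selecting the extreme.
- SAP 6.2 says that same-day repeats are not averaged for shift summaries and that all of them are considered.
- Protocol 8.1.5.2 categorizes values "based on reference ranges of the laboratory used in this study" and counts subjects who have a post-baseline shift during treatment. It has no step that selects a minimum or maximum. SAP 12.1 lists neither the minimum/maximum step nor the per-sample ranges among the changes from the protocol.

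**The concern.** If all of a subject's samples share one range, the largest value is also the one furthest above range, and nothing is lost by looking at it alone. Once results from laboratories with different ranges are pooled, that no longer holds: the largest number may be normal where it was measured, while a smaller number from another laboratory is high. A rule that tabulates only the category of the largest number then records no shift for a subject who had an out-of-range result. The low side works the same way.

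At stake is the completeness of a descriptive safety table. The error runs toward fewer reported abnormalities, and it can arise only in subjects who had local as well as central on-treatment results.

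**Working it through.** The plan gives no figure for this point, so there is nothing to reproduce. The check is of logic, with examples on assumed values and a rough sizing.

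**Two rules compared (high side).** Let x_i be a subject's on-treatment values and U_i the upper limit of the laboratory that ran sample i. The baseline category is the same under both rules.

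- Rule A, the plain reading of SAP 11.3.2: find the sample with the largest x_i, and count a shift if that x_i exceeds its own U_i.
- Rule B, classify first: count a shift if any x_i > U_i. This is the same as max(x_i/U_i) > 1, the form used for the hepatic criteria.

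**Direction.** If the selected maximum exceeds its own limit, then at least one value is high, so A implies B. The reverse can fail. Relative to B, rule A can therefore only undercount. If all U_i are equal, the two rules agree exactly.

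**High-side example (assumed ranges).** Potassium: central 5.2 mmol/L with ULN 5.1, local 5.3 mmol/L with ULN 5.5.

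- Rule A: max(5.2, 5.3) = 5.3, and 5.3 ≤ 5.5, so no shift.
- Rule B: 5.2/5.1 = 1.02 and 5.3/5.5 = 0.96. The larger ratio exceeds 1, so shift to high.

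**Low-side example (assumed ranges).** Central 4.0 and 3.4 with LLN 3.5, local 3.35 with LLN 3.3.

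- Rule A: the minimum is 3.35, and 3.35 ≥ 3.3, so no shift.
- Rule B: 3.4 < 3.5, so shift to low.

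**How abnormal a hidden value can be.** A hidden central value c satisfies U_central < c ≤ local value ≤ U_local, so c/U_central cannot exceed U_local/U_central. In the potassium example the ceiling is 5.5/5.1 = 1.08 times the central ULN. A value above both laboratories' limits cannot be hidden by an in-range local value.

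**Rough size.** The documents give no rate of local testing and no local ranges, so every input here is assumed: a lognormal analyte with median 30, central ULN 40, between-subject log-SD 0.30, within-subject log-SD 0.20, five central on-treatment values, and one local value in 5%, 20% or 100% of subjects, with both laboratories reading on the same scale. About 31% to 34% of subjects with an in-range baseline then have a shift to high under rule B.

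| Local ULN ÷ central ULN | Hidden, among subjects with a local value and a shift under B | Hidden per 80 subjects, one analyte: 5% / 20% / 100% with a local value |
|---|---|---|
| 1.0 | 0% | 0 / 0 / 0 |
| 1.1 | 1.3–1.6% | 0.015 / 0.054 / 0.264 |
| 1.25 | 4.4–5.1% | 0.046 / 0.201 / 0.968 |
| 1.4 | 7.3–7.8% | 0.077 / 0.286 / 1.466 |

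**What else would catch a hidden value.** The maximum toxicity grade summary assigns grades and then takes the worst, so a value just outside range in a direction that Table 9 grades (ALT above ULN, hemoglobin below LLN) still appears there as Grade 1. Sodium, potassium, calcium, magnesium and BUN are in SAP 11.3.1, and so in the shift tables, but not in Table 9. For these the SAP plans only visit values and changes from baseline besides the shift table, and neither is classified against a range.

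**The case against.** The strongest reply is that selecting before classifying is an interpretation. The SAP never says that the extreme is taken on the unscaled value. It states the categorization rule before it mentions the minimum and maximum. SAP 6.2 has all same-day values considered for shifts, the protocol counts any post-baseline shift, and SAP 12.1 announces no departure from that. A programmer could read all this as classify-then-count.

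Part of that stands: the reading is an inference. But SAP 6.2 concerns repeats on one day and leaves the selection across the Treatment Period untouched. The counting rule refers to the maximum and minimum themselves, and nowhere says that any out-of-range value suffices. Where the authors wanted scaling to the range, in the hepatic criteria, they wrote it. The plain reading is therefore the one above, and one sentence would settle it either way.

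A second reply is that classifying every value has its own cost, and this stands. Assume a central baseline of 38 and a later central value of 39 (ULN 40, both normal), plus a local value of 36 (ULN 35, high). Rule B counts a shift to high although 36 is below baseline; rule A does not. Selecting by ratio gives the same result as rule B, since 36/35 = 1.03 exceeds 39/40 = 0.98.

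A third reply is that scheduled samples go to a central laboratory (Protocol 5.3.1.1) and the tables support no test or decision. Both are true, and both limit the size of the problem without removing it.

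**Conclusion.** The point holds as a minor flaw in a stated rule. On the plain reading of SAP 11.3 and 11.3.2, a borderline abnormal value can drop out of the shift table when a subject has results from laboratories with different ranges. On the assumed inputs this amounts to well under one subject per analyte per 80 if 5% to 20% have a local value. It exceeds one only if every subject has a local value and the local limit is 1.4 times the central one. The gap matters mainly for tests outside Table 9.

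Two stronger readings are tempting. A reader might infer that the rule hides the most important results, because extra local testing often follows a serious adverse event. The documents do not support that: a hidden value cannot lie beyond the more permissive laboratory's own limit, so only borderline results are exposed.

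A reader might also take the 4 of 276 subjects with serious events in Protocol Appendix E, scale it to 80 × 4/276 = 1.2 subjects, and call each a miscount. But that rate does not measure local testing. A local result also causes a miscount only if its range is more permissive, its value is numerically more extreme yet in range, and a central value is out of range. No efficacy result is affected.

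**What to change.** Add to SAP 11.3.2, under Shift Tables, that every on-treatment value is first classified as low, normal or high by the range of the laboratory that ran it. A subject then counts as shifted to high (or low) if any on-treatment value is high (or low) and the baseline category was not. Equivalently, select the extreme by ratio to the ULN on the high side and to the LLN on the low side, extending the approach already used for the hepatic criteria.

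This brings the table back to the protocol's count of subjects with any post-baseline shift. It changes counts only where ranges differ within a subject. The cost is one sentence and a change in programming order, with no new data. Because a value no more extreme than baseline may occasionally be flagged, add a short listing of subjects whose on-treatment results come from laboratories with different ranges, showing each value, its range and the baseline.
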